1.0 PURPOSE

1.1 Name and Intended Use

The device used in this study is called the Elite iQ device.

The intended use of the Elite iQ device used in this study is for the treatment of hair removal, pseudo folliculitis barbae, and benign vascular and pigmented lesions.

1.2 Objectives

- 1. Primary Objectives:
 - To assess the safety of the study devices through the collection of side effects throughout the study.
 - To assess efficacy by blinded evaluation of photography.
- 2. Secondary Objectives:
 - To assess of efficacy of the study device through Investigator and subject questionnaires.
 - To assess the ease of use of the new device.

1.3 Duration of the Investigation

The sponsor anticipates that all subjects can be enrolled within 3 months. If subject participates in all required visits, then the subject's participation in this study may last up to 15 months. It is anticipated that it will take approximately 3 months to analyze the data collected during this study. The total duration of this study is anticipated to last approximately 21 months.

2.0 PROTOCOL

2.1 Protocol Methodology and Analysis

Methodology:

Subjects are to be enrolled in this clinical study if they are a healthy male or female 18 years of age or older. Up to 20 subjects will be enrolled at up to 1 study center. Subjects will attend a screening/pretreatment visit which may be performed on the same day as the treatment visit. Subjects may receive up to 5 treatments on multiple areas of the body such as, but not limited to, the face, legs, and arms. All subjects will be required to return a follow-up visit at 30 - 90 days after the final treatment in each treatment area. An unscheduled visit or phone call may be performed at any time during the study at the request of the subject or as deemed necessary by the site Investigator.

Analysis:

Upcoming generations are proving to have an interest in non-ablative aesthetic treatments and will drive demand for innovated products, procedures, and practice design. Due to this shift in patient base, practices need to evolve to adapt to the newer generational ideologies. This device uses the Alexandrite wavelength (755 nm) and the Nd:YAG wavelength (1064 nm) target hair follicles, unwanted veins, pigmented lesions and treat sun-damaged skin. Although this laser technology is one of the most used, there is a need for a new advanced treatment guidance system that is built into the laser.

Relevance:

According to the 2018 Plastic Surgery Statistics Report, the amount of laser treatments for minimally invasive aesthetic treatments have drastically increased over the past 8 years.² There is an increasing demand for new methods and novel laser technology for improved treatment outcomes. Other devices currently on the market cleared for use include, but are not limited to, the Excel and Candela devices.

Testability:

The Elite+ device, the most current approved Elite platform, had been previously cleared for use for hair reduction and the treatment of vascular lesions, benign pigmented lesions, pseudo folliculitis barbae, and wrinkles (FDA K141425). This study will utilize similar evaluation methods to assess prototype software and accessories.

Compatibility:

Although laser technology is a well-known and widely use technique for non-ablative aesthetic treatments, there is still a need to improve technology to reduce the number of treatments and provide a more effective treatment plan.

Predictive power:

Assuming there is significant improvement, it would be appropriate to expect results in different areas where other products and devices have significant results alongside more effective treatments for hair removal, pseudo folliculitis barbae, and benign vascular and pigmented lesions.

2.2 Protocol Study Design

This is a prospective, open label, single-center clinical study to collect safety and efficacy data on the Elite iQ workstation.

2.3 Subject Selection Criteria

Subjects will meet the criteria described below:

Inclusion Criteria:

- A healthy male or female 18 years of age or older.
- Understands and accepts obligation not to receive any other procedures on the treatment area through the length of the study.
- Understands and accepts the obligation and is logistically able to be present for all visits.
- Is willing to comply with all requirements of the study and sign the informed consent document.

Exclusion Criteria:

- The subject is hypersensitive to light in the near infrared wavelength region
- The subject has sun-damaged skin (treatment contraindicated with Alex laser only)
- The subject had recent unprotected sun exposure (for Alex laser within four weeks of treatment; for Nd:YAG laser within one week of treatment), including the use of tanning beds or tanning products, such as creams, lotions and sprays

- The subject is taking medication which is known to increase sensitivity to sunlight
- The subject has seizure disorders triggered by light
- The subject is taking anticoagulants
- The subject is taking or have taken oral isotretinoin, such as Accutane®, within the last six months
- The subject is taking medication that alters the wound-healing response
- The subject has a history of healing problems or history of keloid formation
- The subject has an active localized or systemic infection, or an open wound in area being treated
- The subject has a significant systemic illness or an illness localized in area being treated
- The subject has a history of skin cancer or suspicious lesions
- The subject has an autoimmune disease
- The subject is receiving or have received gold therapy
- The subject is currently enrolled in an investigational drug or device trial, or has received an investigational drug or been treated with an investigational device within in the area to be treated 6 months to entering this study.
- The subject has any condition or is in a situation which in the investigators opinion may put the subject at significant risk, may confound study results or may interfere significantly with the subject's participation.

Be sure to list all concomitant medications taken or procedures performed before, during and after the trial.

Subjects will be recruited for the study through the existing patient database and may use advertisements.

Subject populations will not be eligible to participate in the study if they are vulnerable populations such as children, pregnant women, prisoners, institutionalized individuals, and any persons requiring a legally authorized representative as part of the consenting process.

Subject population characteristics that will not be eligible to participate in participate in the study include non-English speaking individuals and people who cannot read or comprehend English. Employees of the Investigator will be participating in the study.

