2.13 Evaluation Methods

Photographs:

Photographs will be taken at all visits and will be used to assess safety and efficacy of treatment.

Treatment Discomfort/Pain Evaluation:

Subjects will be asked to report the general level of treatment discomfort on a scale of 0 (none) to 10 (maximum intolerable pain) using the universal pain assessment tool (Appendix B)

Subject Questionnaire:

The subject will be asked their level of satisfaction using a 6-point Likert scale that ranges from "extremely satisfied" to "extremely unsatisfied."

Subject Satisfaction		
Rating	Description	
6	Extremely Satisfied	
5	Satisfied	
4	Slightly Satisfied	
3	Slightly Unsatisfied	
2	Dissatisfied	
1	Extremely Unsatisfied	

Physician Questionnaire:

The Clinical Global Aesthetic Improvement Scale (CGAIS) ranging from "worse" to "very much improved" will be used to judge the improvement as seen by the treating Investigator.

Global Aesthetic Improvement Scale Assessment		
Rating	Description	
1	Very Much Improved- Optimal cosmetic result in this subject	
2	Much Improved- Marked improvement in appearance form the initial	
condition, but not completely optimal for this subject.		
3	Improved- Obvious improvement in appearance from initial condition, but a re-treatment is indicated.	
4	No Change- The appearance is essentially the same as the original condition.	
5	Worse- The appearance is worse than the original condition.	

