2.15 Statistical Analysis

2.15.1 Hypothesis

For this study to be considered a success, parameters are developed, and the side effect profile is acceptable to the Physician as it relates to this type of treatment.

For secondary objectives to be considered a success, the results from any assessments will need to be statistically significant or have $\geq 80\%$ response rate. In cases where the subject's improvement is being graded on a scale, such as the GAIS scale, we will test the statistical significance of our results against a hypothetical population that would have no change (average score of 4).

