2.15.6 Analysis of Safety Variables

Safety will be assessed through the degree of pain/discomfort related to the procedure (universal pain scale) and the collection of Adverse Events throughout the course of the study. For each treatment group these variables will be summarized. The summaries will include the number and percent of patients for each outcome. No statistical comparisons will be performed for any of these variables.

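### Section 2.3 as written enrols the Investigator's own employees; either a 'not' is missing, or the plan admits subjects whose ratings can bias the unblinded results and does not separate them

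*Combined protocol and SAP*

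**What the plan says.** Section 2.3 (Subject Selection Criteria) lists who cannot take part: "vulnerable populations such as children, pregnant women, prisoners, institutionalized individuals, and any persons requiring a legally authorized representative", then people who cannot read or comprehend English. The next sentence is "Employees of the Investigator will be participating in the study". It gives no number, cap or condition. On the source of subjects, the same section says: "Subjects will be recruited for the study through the existing patient database and may use advertisements". Employees are not mentioned there.

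Section 2.2 describes the design: "This is a prospective, open label, single-center clinical study to collect safety and efficacy data on the Elite iQ workstation".

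The outcomes that such subjects would supply or influence are these:
- **Satisfaction** (2.13): "The subject will be asked their level of satisfaction using a 6-point Likert scale".
- **Pain and adverse events** (2.15.6): "Safety will be assessed through the degree of pain/discomfort related to the procedure (universal pain scale) and the collection of Adverse Events". The pain score is the subject's own, from 0 to 10 (2.13).
- **CGAIS**: graded by the treating Investigator (2.13) and named as the primary efficacy variable in 2.15.5, although section 1.2 gives blinded photograph evaluation as the primary efficacy objective.

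Section 2.15.1 sets the secondary success rule: "For secondary objectives to be considered a success, the results from any assessments will need to be statistically significant or have" a response rate of at least 80%. Overall success requires that parameters are developed and that the Physician finds the side effect profile acceptable.

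**The concern.** A sentence that admits a group, placed straight after text that shuts groups out, reads like a slip. It may not be one, and a site that follows the protocol literally may enrol its own staff.

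If it does, those subjects know what they received, are treated by their employer, and may want a good result or feel that one is expected. The likely direction is higher satisfaction, lower pain scores and fewer complaints volunteered between visits. The CGAIS adds a second route: the employer grades the improvement of his or her own staff without blinding. Under section 14.0 the Investigator or study staff also rate the relationship of each adverse event to the device, so an employee's event may be judged by an employer or colleague.

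With at most 20 subjects at one site, each person is 1/20 = 5 percentage points of a response rate, so a handful of employees can matter. The documents contain no cap, no independent rater and no analysis without employees, so the report could not show whether they made a difference.

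**Working it through.** **Step 1. Reading the sentence.** Two readings fit section 2.3.
- *A 'not' is missing.* The sentence closes a paragraph on ineligible groups, and employees are absent from the recruitment sources. Both points favour this reading.
- *It is intended.* The wording is affirmative and sits under subject selection.

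A third reading, that it only describes staff who work on the trial, does not fit a paragraph on subject eligibility. All three need a correction or a clarification.

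**Step 2. Which outcomes are exposed, if it is intended.**

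| Outcome | Who supplies it | Exposed? |
|---|---|---|
| Satisfaction (2.13) | Subject | Yes |
| Pain (2.13, 2.15.6) | Subject | Yes |
| Adverse events (2.14, 14.0) | Documented and rated by Investigator or staff; between visits, largely dependent on the subject reporting them | Partly |
| CGAIS (2.13, 2.15.5) | Treating Investigator, unblinded | Yes |
| Blinded photographs (1.2, 3.2) | Evaluators outside the study | Largely protected |

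**Step 3. What can be calculated.** The plan's only relevant figure is the total of 20 subjects, including departures (2.15.2). It comes with no effect size, SD, power or dropout rate, so it cannot be reproduced. The number of employees is not stated, so the real bias cannot be computed. What follows is an illustration for the 80% route only.

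Inputs from the plan: 20 subjects and the 80% threshold, so 0.80 × 20 = 16 responders.

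Assumptions:
- All 20 are evaluable, and a response is a positive rating (the plan does not define response for satisfaction).
- k subjects are employees, who rate positively with probability q.
- The other 20 − k rate positively with probability p, and ratings are independent.

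Formula: P(X + Y ≥ 16), with X ~ Binomial(k, q) and Y ~ Binomial(20 − k, p). For k = 5 and q = 1 this reduces to P(Binomial(15, p) ≥ 11).

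| p (others) | q (employees) | k = 0 | k = 2 | k = 5 |
|---|---|---|---|---|
| 0.70 | 0.70 | 0.238 | 0.238 | 0.238 |
| 0.70 | 0.80 | 0.238 | 0.268 | 0.318 |
| 0.70 | 0.90 | 0.238 | 0.300 | 0.411 |
| 0.70 | 1.00 | 0.238 | 0.333 | 0.515 |
| 0.60 | 0.60 | 0.051 | 0.051 | 0.051 |
| 0.60 | 0.90 | 0.051 | 0.082 | 0.160 |
| 0.60 | 1.00 | 0.051 | 0.094 | 0.217 |

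The expected response rate is (kq + (20 − k)p)/20. For p = 0.70, q = 0.90 and k = 5 it is (4.5 + 10.5)/20 = 0.75, against 0.70 without employees.

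The rows with q = p show the limit of the argument: employees who answer like everyone else change nothing.

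**The case against.** The strongest reply is that the case rests on one sentence that may be a typing error, with an unknown number of employees whose answers are also unknown. If a 'not' was dropped, a one-word correction settles the matter and the bias argument falls away. That is right, and it is why the first request is to settle the sentence. It is not a reason to leave the sentence as it stands.

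A reader might infer more than the documents support:
- *That the results are biased toward success.* Only a risk with a likely direction is shown. Neither k nor q is given.
- *That the probabilities above are the chance of secondary success.* They are not. Section 2.15.1 allows statistical significance as an alternative to 80%, so missing 80% is not failing.
- *That side effects are self-reported and alone decide study success.* The Investigator or staff document and rate adverse events, and photographs also serve safety (2.13). Overall success also requires that parameters be developed, and the acceptability of the side effect profile is a physician's judgement with no numeric threshold.

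Safeguards exist. Photograph evaluation is to be blinded (1.2, 3.2), the Investigator's compensation does not depend on the outcome (3.2), an IRB reviews the protocol (8.0), and subjects may withdraw without penalty (12.0). The Investigator may also exclude anyone whose situation could confound the results (2.3). These protect the photographs and the subjects' freedom to leave. They do not protect satisfaction, pain, spontaneous reporting or the CGAIS, and the discretionary exclusion rests with the employer. The CRF and consent form are attachments not in view, so a flag could exist there; the protocol mentions none.

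**Conclusion.** The point stands as a defect in a stated eligibility rule, to be settled before enrolment. Either the rule is wrong as written, or the plan admits a group whose ratings, and whose grading by their employer, can bias satisfaction, pain, adverse-event reporting between visits and the CGAIS. Blinded photograph evaluation is largely unaffected.

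The size is unknown. Under the stated assumptions and a 70% true rate in other subjects, the chance of reaching 80% goes from 0.24 with no employees to 0.30 to 0.33 with two and 0.41 to 0.52 with five, for employees who rate positively 90% to 100% of the time. With a 60% true rate and employees at 90%, it goes from 0.05 to 0.16 with five. The documents do not show that bias will occur, and these figures should not be cited as if they did.

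**What to change.** **Preferred.** Replace the sentence in 2.3 with one that makes employees of the Investigator ineligible. This is right if a 'not' was dropped and removes the risk if it was not. The cost is one eligibility line and possibly slightly slower recruitment.

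**If the sponsor keeps them:**
1. State in 2.3 that the inclusion is intended, and flag employee status on the CRF.
2. Keep every treated subject in the main safety and intention-to-treat analyses. Section 2.15.3 counts everyone who begins treatment, and drawing the safety conclusions from a set without employees could hide events.
3. Pre-specify a sensitivity analysis without employees for satisfaction, pain, CGAIS and adverse events, reported beside the full set.
4. Claim success on satisfaction or CGAIS only if it also holds without employees.

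The cost is one CRF field and one repeated set of tables. The reduced set is also smaller: with five employees among 20 it has 15 subjects, and 80% means 0.80 × 15 = 12 responders, so its result is less precise.

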2.4 Screening

Subjects will be asked questions about their medical history, may have a limited physical and their inclusion/exclusion criteria will be verified. Discontinuation of any concomitant medications, pretreatment instructions and post treatment instruction will be reviewed with the subject.

Procedure for the Limited Physical Exam:

If the investigator determines that a limited exam is necessary, the exam will be like a basic annual physical exam performed by a primary care doctor to determine general overall health. The limited medical exam may include all or any of the following; vital signs such as blood pressure, heart

rate, respiratory rate and body temperature, general appearance, listening to the heart, lungs and abdomen with a stethoscope, head and neck exam, in addition to examining the throat, tonsils, teeth, ears, eyes and nose as well as a neurological exam such as testing muscle strength, reflexes, balance, sensory changes of the extremities and mental state.

2.5 Informed Consent Process and Enrollment

Subjects will be asked to review the pre and post treatment instructions prior to signing the informed consent form and their involvement in the study. Subjects who sign the informed consent will be screened to confirm eligibility and, if eligible, will be assigned a subject identification number. Subjects will be de-identified through their subject identification number, which will be stored in a secure location. Subject identification numbers will be generated chronologically and assigned only to subjects who have met all the study selection criteria and have signed the informed consent form. The informed consent will be obtained prior to a subject's involvement in any study related procedures. A subject will be considered enrolled in the study once they have signed the informed consent form.

2.6 Pre-Treatment Procedures

If the subject is of childbearing potential (i.e. females not post-menopausal or not surgically sterile), they will be asked if they are pregnant, the date of their last menstrual cycle, and perform a urine pregnancy test. A urine pregnancy test will be performed on all women of childbearing potential prior to each treatment only if the treatment is on the abdomen. A urine pregnancy test may also be conducted at the Investigator's discretion at any time during the study. If a urine pregnancy test is conducted, then a negative result must be obtained within 24 hours prior to the treatment.

Urine Pregnancy Test Procedure:

- 1. A urine sample is tested mid-stream or by cup sample with an indicator stick.
- 2. Negative results are indicated on the indicator stick.
- Photographs will be taken prior to the first treatment and may be taken prior to each subsequent treatment.
- The following Pre-Treatment instructions will be reviewed:
 - For hair removal subjects, you will be asked to grow hair in the treatment area for a minimum of 5-7 days prior to the baseline photos.
 - o For all other treatments and subsequent hair removal treatments, shave any visible hair on the area to be treated 24 hours before treatment.
 - Avoid sun exposure, including tanning beds, self-tanning lotions/creams/sprays for a at least 4 (four) weeks before, and during and after (at least one week) the course of laser treatments
 - o Remove all makeup, lotions, deodorant, and oil from the area to be treated.

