2.7 Treatment Procedures

- The defined study area will be identified and may be marked with a white or yellow, washable marker.
- A topical anesthetic may be applied to the treatment area prior to treatment.

- To avoid eye injury, appropriate eye protection for the wavelength being used must be worn by all individuals in the room during treatment.
- Test spots should be performed prior to each treatment.
- The Skintel Melanin Reader will be used for objective measurement of the melanin content of skin. The Skintel Reader will provide guidance to help select test spot settings.
- Procedures for the Elite iQ treatment:
 - o The device will be used in accordance with the Operator's Manual.
 - Pulses will be delivered in a linear fashion with no more than a 10% overlap between pulses.
 - An air-cooling system may be used during treatment. The air-cooling system allows for the continuous flow of cold air on the treatment area to ease the sensation from the laser pulse.
 - A thin coating of gel, aqueous or surgical lubricant, clear aloe, clear ultrasonic gel, or water can be used in conjunction with the system as a conduit for the laser energy and to increase cooling efficiency of the treatment site.
 - Parameters may be adjusted throughout the treatment in order to increase subject comfort.
 - O Subjects will be asked to report the general level of treatment discomfort/pain on a scale of 0 (none) to 10 (maximum intolerable pain).
 - o Parameters and skin reaction will be continuously monitored and recorded during treatment.
- The additional treatments will follow the same procedure.
- Subjects may receive between 1-5 treatments on each treatment area. Subjects may return for a treatment visit every 2-10 weeks.

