2.8 Post Treatment Procedures

- Adverse events will be documented after treatment.
- Following treatment, an aloe-based gel, chiller, and/or cold pack may be applied to soothe the skin.
- Photographs may be taken post treatment.
- The following post treatment instructions will be reviewed with subject:
 - Wash the treatment area gently with soap and water. Do not soak. Gently pat area to dry.
 - o Following treatment, apply an aloe-based gel or equivalent (such as a cold pack) to soothe and moisturize the skin.
 - o Do not shave the treated area if blistering or crusting is evident.
 - o Avoid contact sports or any other activity that could cause bruising of the treated area.
 - o Following the laser treatment, activities, such as swimming, sports, or strenuous exercise should be avoided for the first 2–3 days, or until any redness, crusting, or blisters have resolved.
 - o For vein treatment, avoid exercises that can cause vasodilatation for 1-week posttreatment. Walking is encouraged after vein treatment.
 - Avoid sun exposure throughout the course of treatment and use a broad-spectrum (UVA/UVB) sun block SPF 30 or greater when treatment area is exposed to the sun.

- Avoid sun exposure as delayed secondary blistering has been noted up to 72 hours posttreatment.
- Contact physician if there is any sign of blistering or infection (redness, tenderness, or pus).
- o An antibiotic cream should be used if there is any blistering or break in the skin.
- o Do not use tanning beds.
- o Avoid hot baths/whirlpools for 1 week following treatment (vein treatment).
- Normal skin care regimens, i.e., makeup, moisturizers, deodorant, and shaving may be resumed the day after treatment if there is no redness, blistering, or crusting present. If makeup is allowed, apply and remove it delicately. Excess rubbing can open the area and increase the chance of scarring. If the area blisters, extreme caution should be used when applying or removing makeup. The treated area is very delicate and should be treated with care.
- o For vein treatment, discomfort, such as swelling or redness (lasting from a few hours to a couple of days), can be relieved with acetaminophen (such as Tylenol) or ice packs.
- Apply lotion to the area to prevent drying and crusting. Lotion applied following the laser treatment can have a soothing effect. If a crust develops, allow it to fall off naturally. Do not scratch or pick (vein treatment).

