2.9 Follow Up

- The study subjects are required to return to Investigator site for a follow up evaluation between 30 90 days post last treatment.
- Subject and Investigator questionnaires may be performed at these visits.
- Photographs will be taken, and adverse events will be documented at all follow up visits.
- Some subjects may have an incomplete response or no response by the end of the study. At the end of the study, treatments using an FDA approved/cleared treatment method may be discussed with the subject and obtained at the cost of the subject.

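### For hair-removal areas the protocol body sets a hair-growth condition for the baseline photographs but none for the Visit 7 photographs

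*Combined protocol and SAP*

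**What the plan says.** One of the primary objectives in section 1.2 is "To assess efficacy by blinded evaluation of photography". Section 2.2 states "This is a prospective, open label, single-center clinical study" and describes no control arm.

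The instructions that bear on hair are these:

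- Section 2.6, before the baseline photographs of hair-removal subjects: "you will be asked to grow hair in the treatment area for a minimum of 5-7 days prior to the baseline photos".
- Section 2.6, before treatment: "For all other treatments and subsequent hair removal treatments, shave any visible hair on the area to be treated 24 hours before treatment".
- Section 2.8, after treatment: "makeup, moisturizers, deodorant, and shaving may be resumed the day after treatment if there is no redness, blistering, or crusting present". The same section rules out shaving while there is blistering or crusting. It names no later point at which shaving should pause.

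On the follow-up photographs, section 2.9 says "Photographs will be taken, and adverse events will be documented at all follow up visits". The schedule in section 2.12 marks photographs at Visit 7 and no treatment there. Section 2.13 says that the photographs serve both safety and efficacy. Section 13.0 has camera settings reproduced from visit to visit so that the images can be compared, and has the subject take off jewelry, make-up and lotions before each session. None of these four sections mentions hair growth or shaving.

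**The concern.** By asking for growth before the baseline photographs, the plan itself treats hair length as a condition of a usable image. It then leaves that condition open for the other half of each pair. Reproducing lighting and distance does not make an area with about a week of growth comparable with one shaved that morning, or with one left alone for two months.

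Blinding does not remove the problem, because the difference lies in the image. Section 3.2 requires evaluators who took no part in the study, and the plan does not say that they are told when the subject last shaved. With no control arm described, no parallel group is exposed to the same artifact and could offset it.

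The physician's CGAIS rating, which section 2.15.5 calls the primary efficacy variable, also looks back to the starting condition. It is less exposed, since the treating Investigator sees the subject and can ask about shaving. The main stake is therefore the blinded photographic evaluation of hair-removal areas.

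**Working it through.** The plan gives no figure to reproduce here. The check is a comparison of the text, followed by a small illustration.

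**Does any instruction reach the Visit 7 photographs?**

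1. The growth instruction in section 2.6 is tied by its own words to the baseline photographs.
2. The 24-hour shaving instruction in section 2.6 is tied to treatments. Visit 7 has none (2.12).
3. Section 2.8 governs skin care after a treatment. It permits shaving once the skin is clear and sets no pause before follow-up.
4. Section 2.3 asks that the subject "Understands and accepts obligation not to receive any other procedures on the treatment area through the length of the study". Since section 2.8 expressly allows shaving, this cannot be read as a ban on it.
5. The list in section 13.0 that ends in an open et cetera is a list of camera settings. Subject preparation has its own sentence, and hair is not in it.

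So nothing in the protocol body controls time since last shave at Visit 7.

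**Illustration of a mismatched pair**

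Inputs: baseline growth of 5-7 days, the stated minimum (2.6); Visit 7 at 60 +/- 30 days after the last treatment (2.12), so 60 - 30 = 30 to 60 + 30 = 90 days. Difference = days since last shave at Visit 7 minus days of growth at baseline.

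- Shaved on the day of Visit 7 or the day before (0-1 day): from 0 - 7 = -7 to 1 - 5 = -4 days. The pair leans towards apparent hair reduction.
- Last shaved at about the time of the last treatment (30-90 days): from 30 - 7 = +23 to 90 - 5 = +85 days. The pair leans against the device.

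If regrowth were linear and treatment had no effect (both assumptions, for scale only), 1 day against 5-7 days is 1/7 to 1/5, or about 14% to 20% of the baseline length. At the other end, 30/7 = 4.3 and 90/5 = 18, so about 4 to 18 times the baseline length.

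**Why these are not limits**

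- Section 2.6 gives baseline growth a minimum and no maximum. A subject with, say, 30 days of growth at baseline who shaves on the day of Visit 7 has a difference of 0 - 30 = -30 days.
- The shave before later treatments applies to visible hair only, so a subject with none has no reason to shave then.
- "Subjects may receive between 1-5 treatments on each treatment area", and section 2.6 states no shave before the first hair-removal treatment. After a single treatment the last shave may therefore date from before baseline.
- Section 2.12 allows screening on the day of the first treatment but does not require it, so baseline photographs may come earlier.

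The documents give neither the number of hair-removal subjects among the 20 nor any shaving rate. The average bias cannot be calculated.

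**The case against.** The strongest objection is that a missing rule has not been proved. The growth instruction sits in a list of pre-treatment instructions, where nobody would look for a follow-up rule. Section 7.0 shows that subjects receive separate Pre and Post Treatment Instructions and an Informed Consent Form. Those two, the Operator Manual, the Clinical Reference Guide and the Case Report Form (Attachments I to V) were not available here, and any of them could hold the rule. This stands, and it confines the point to the protocol body. It does not answer why section 13.0, which sets subject preparation for every photo session, omits hair.

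Second, section 13.0 calls the photographs standardized, and the plan provides for site training. That shows an intention to obtain comparable images, but it gives the site no interval to apply.

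Third, the consequence is modest. Overall success in section 2.15.1 turns on developing parameters and an acceptable side-effect profile. Sections 2.13 and 2.15.5 also define no photographic grade or analysis, so there is as yet no result to recompute without the mismatched pairs. Both remarks stand. The first limits the weight of the point, and the second limits the remedy to listing such pairs.

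A reader might also infer that the gap systematically favors the device, since subjects used to shaving before treatment visits may do so before the last visit. The documents give no shaving rate, and they equally permit long growth. No direction can be claimed.

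**Conclusion.** The point holds for the protocol body: followed as written, the plan allows baseline and Visit 7 photographs of hair-removal areas that are not comparable in time since last shave, and these photographs serve a primary objective. An asymmetric growth condition combined with express permission to shave can produce apparent hair reduction or conceal a real one.

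The size is unknown and the sign is not fixed. The differences of -7 to -4 days and +23 to +85 days are illustrations that assume 5-7 days of growth at baseline. They are neither bounds nor expected values.

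Two stronger readings are not supported. One is that the study's success is in doubt; section 2.15.1 does not rest on the photographs, and vascular and pigmented-lesion areas are unaffected. The other is that no rule exists anywhere; the attachments could not be checked. The change should be made, with medium confidence because of those attachments.

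**What to change.** In sections 2.9 and 13.0, ask hair-removal subjects to come to the Visit 7 photographs with the same time since last hair removal as at their own baseline photographs, within a tolerance fixed in advance. Matching to the subject's own baseline limits both fresh shaving and long growth, whereas repeating an open-ended minimum would limit only the first. This is a condition on the measurement and leaves the skin-care and shaving instructions around treatment as they are.

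Record the date of last hair removal at the baseline and Visit 7 photo sessions. When the photographic evaluation is reported, list the pairs that do not match, including any for which a date is unknown. If one of the attachments already contains such a rule, a cross-reference in 2.9 and 13.0 is enough. The rule needs to be in place before the first Visit 7, because photographs taken under unmatched conditions cannot be retaken.

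The cost is about a week unshaved before the last visit (longer if the subject's baseline growth was longer), one or two fields on the Case Report Form, and a protocol revision with the written IRB approval that section 21.0 requires.
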